5.7.5. Analysis of MRI Variables

Descriptive statistical analyses for the MRI variables defined in Section [4.7.5](#) will be summarized by treatment group and overall for the study, as well as by treatment group and overall within each cohort in the MRI population.

For descriptive summaries, raw values, percent change, and/or when appropriate, absolute change from baseline will be provided for MRI variables at each protocol scheduled time point (as defined by e-CRF visit label) for each treatment group. Missing values will not be imputed. For the evinacumab treated group, within-patient testing of endpoints with a non-normal distribution will use the Wilcoxon signed-rank test and endpoints with a normal distribution will use the paired t-test to evaluate the mean differences between baseline and each protocol visit. The p-value will be provided for descriptive purposes only

5.8. Analysis of Safety Data

The summary of safety results will be presented separately for the DBTP and SBTP, unless otherwise noted. Safety summaries for the DBTP will be presented by treatment groups (evinacumab, placebo), as well as by treatment group within each cohort containing patients from the double-blind safety analysis set. Safety summaries for the SBTP will be presented by all patients and by treatment group in DBTP (i.e., evinacumab, placebo), for patients in the single-blind safety analysis set. No formal inferential testing will be performed for either period. Summaries will be descriptive in nature.

General common rules

All safety analyses will be performed, unless otherwise specified, using the following common rules:

- Safety data in patients who do not belong to the safety analysis set (i.e., exposed but not randomized) will be listed separately.
- PCSV values are defined as abnormal values considered medically important by the Sponsor according to predefined criteria/thresholds based on literature review and defined by the Sponsor for clinical laboratory tests and vital signs (PCSV version dated January 2009 [[Appendix 10.3](#)]). Considering that the threshold defined in the PCSV list for monocytes and basophils can be below the ULN, the following PCSV criterion will be used for the PCSV analysis of monocytes and basophils:
 - PCSV criterion for monocytes: >0.7 Giga/L or $>\text{ULN}$ (if $\text{ULN} \geq 0.7$ Giga/L).
 - PCSV criterion for basophils: >0.1 Giga/L or $>\text{ULN}$ (if $\text{ULN} \geq 0.1$ Giga/L).
- PCSV criteria will determine which patients had at least 1 PCSV during the respective TEAE periods, taking into account all evaluations including unscheduled or repeated evaluations.
- For summary tables, only protocol scheduled measurements (as defined by e-CRF visit label) will be included. Patient listings will include all measurements, scheduled and unscheduled.
- The treatment-emergent PCSV denominator by treatment group for a given parameter will be based on the number of patients assessed for that given parameter at least once during the respective TEAE periods.
- For quantitative safety parameters including central laboratory measurements and vital sign scores, descriptive statistics will be used to summarize observed values and change from baseline values by visit.

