4.2.2. Secondary Endpoints

The secondary endpoints of the study are:

- Percent TG lowering from baseline following 2 to 24 weeks of repeated IV doses of evinacumab overall and subgroups with homozygous or compound heterozygous LOF mutations, heterozygous LOF mutations, and without LOF mutations in genes in the LPL pathway
- Changes in patient reported abdominal and GI symptoms, dietary habits, and symptom/dietary impact measures

- Degree of pancreatic injury/inflammation through ¹⁸F-FDG-PET imaging at baseline (placebo run-in) and change from baseline following 12 weeks of treatment with evinacumab as assessed by ¹⁸F-FDG standardized uptake values SUV_{max} and SUV_{mean}
- Degree of pancreatic injury/inflammation through DW-MRI at baseline (placebo run-in period) and the change from baseline following 12 and 24 weeks of treatment with evinacumab as assessed by ADC
- The total evinacumab concentrations, total ANGPTL3 concentrations, and ADA during the evinacumab treatment and follow-up periods
- Incidence and severity of treatment-emergent adverse event (TEAEs), SAEs, laboratory abnormalities, and other safety variables in patients treated with evinacumab

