10.4.5. Safety Analysis

10.4.5.1. Adverse Events

Definitions

For safety variables, 3 observation periods are defined:

- The pretreatment period is defined as the time from signing the ICF to before the first dose of study drug
- The treatment period is defined as the day from first dose of randomized study drug to end of the study

- The double-blind treatment period is defined as the day from first dose of study drug in the double-blind treatment period to the day prior to the administration of single-blind evinacumab

Treatment-emergent adverse events are defined as those that are not present at baseline or represent the exacerbation of a pre-existing condition during the on-treatment period.

Analysis

All AEs reported in this study will be coded using the currently available version of MedDRA. Coding will be to lowest level terms. The verbatim text, the preferred term (PT), and the primary system organ class (SOC) will be listed.

Summaries of all TEAEs will include:

- The number (n) and percentage (%) of patients with at least 1 TEAE by SOC and PT
- TEAEs by severity (according to the grading scale outlined in Section 9.5.1), presented by SOC and PT
- TEAEs by relationship to treatment (related, not related), presented by SOC and PT

All deaths, SAEs and TEAEs overall and events leading to permanent treatment discontinuation will be listed will be listed.

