4.8.1. Adverse Events Variables

The period of safety observation starts from the time when the patient gives informed consent and continues into the following periods:

- The PRE-TREATMENT period is defined from the day the ICF is signed to the day before the first dose of double-blind study treatment administration.
- The double-blind treatment-emergent adverse event (TEAE) period is defined from the day of the first dose of double-blind study treatment administration to the day of the last dose of double-blind study treatment administration + 168 days (24 weeks) for those patients not proceeding into the SBTP, or up to the day before the first dose of single-blind study treatment administration for those patients proceeding into the SBTP.
- The single-blind treatment-emergent adverse event (TEAE) period is defined from the day of the first single-blind study treatment administration to the day of the last single-blind study treatment administration + 168 days (24 weeks).
- The POST-TREATMENT period is defined from the day after the end of the respective TEAE periods to the last study visit.

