5.8.1. Adverse Events

In general, the primary focus of AE reporting will be on TEAEs summarized in respective TEAE periods, specifically the DBTP and SBTP. Post-treatment AEs will be summarized separately.

If an AE onset date (occurrence, worsening, or becoming serious) is incomplete, an imputation algorithm will be used to classify the AE as pre-treatment, treatment-emergent, or post-treatment. The algorithm for imputing date of onset will be conservative and will classify an AE as treatment-emergent unless there is definitive information to determine pre-treatment or post-treatment status. Details on classification of AEs with missing or partial onset dates are provided in [Section 6.2](#).

Adverse event incidence tables will present the number (n) and percentage (%) of patients experiencing an AE by SOC and PT. Multiple occurrences of the same event in the same patient will be counted only once in the tables within a treatment phase (TEAE or post-treatment AE). For tables presenting severity of events, the worst severity will be chosen for patients with

multiple instances of the same event. The denominator for computation of percentages is the respective safety analysis set within each treatment group.

AE incidence tables will present data by SOC sorted alphabetically and PT sorted by decreasing frequency of the evinacumab treated group and summarize the number (n) and percentage (%) of patients experiencing an AE.

Analysis of all treatment-emergent adverse events

The following TEAE summaries will be generated:

- Overview of TEAEs, summarizing number (%) of patients with any
 - TEAE;
 - Serious TEAE;
 - TEAE leading to death;
 - TEAE leading to permanent treatment discontinuation.
- All TEAEs by primary SOC and PT
- Number (%) of patients experiencing any TEAE(s) presented by primary SOC and PT
- All TEAEs relationship (related/not related) to evinacumab
- All TEAEs by maximum severity (i.e., mild, moderate or severe)

Analysis of all treatment emergent serious adverse event(s)

- All Serious TEAEs by primary SOC and PT
- Patient listings of serious TEAEs will be provided in the report appendix
- All Serious TEAEs relationship (related/not related) to evinacumab

Analysis of all treatment-emergent adverse event(s) leading to treatment discontinuation

- All TEAEs leading to permanent treatment discontinuation, by primary SOC and PT
- Patient listings of TEAEs leading to permanent treatment discontinuation will be provided in the report appendix

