5.8.2. Analysis of Adverse Events of Special Interest

Treatment-emergent adverse events of special interest (AESI), as listed in Section 4.8.1.2, will be presented by SOC and PT, if applicable. AESI are defined by SMQ, CMQ, dedicated e-CRF, or lab data as described in [Appendix 10.2](#).

The following variables will also be tabulated for infusion reactions TEAEs:

- Intensity of the event (mild, moderate, and severe);
- Number of events divided by the number of study treatment administrations received in respective treatment periods;
- Time from first study treatment administration (DBTP or SBTP depending on the analysis) to first infusion reaction;

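### No planned safety table gives per-patient incidence over all evinacumab exposure, and in the single-blind analysis the infusion-reaction clock of evinacumab-first patients starts at their fourth dose

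*SAP*

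**What the plan says.** Protocol 4.2.2 lists as a secondary endpoint the incidence and severity of adverse events, together with "laboratory abnormalities, and other safety variables in patients treated with evinacumab". Protocol 10.4.5.1 works with one long safety window: "The treatment period is defined as the day from first dose of randomized study drug to end of the study".

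The SAP splits this by period and declares the change in section 1.2.4, item 3. SAP 5.8: "The summary of safety results will be presented separately for the DBTP and SBTP, unless otherwise noted". Double-blind safety is shown by arm. Single-blind safety is shown for everyone and, separately, by former double-blind arm. SAP 5.8.1 says that "the primary focus of AE reporting will be on TEAEs summarized in respective TEAE periods, specifically the DBTP and SBTP", counts a repeated event once per patient within a treatment phase, and takes the period's own safety set as denominator. SAP 4.8.1 fixes the second window: "The single-blind treatment-emergent adverse event (TEAE) period is defined from the day of the first single-blind study treatment administration", running to 168 days after the last single-blind dose.

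For infusion reactions, SAP 5.8.2 plans two period-specific measures: "Number of events divided by the number of study treatment administrations received in respective treatment periods", and "Time from first study treatment administration (DBTP or SBTP depending on the analysis) to first infusion reaction".

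Data are joined across periods, or aligned to the start of evinacumab, only outside safety. The triglyceride model re-aligns visits to the start of evinacumab (SAP 5.7.1). Exposure is cumulated for patients on evinacumab in the double-blind period (SAP 4.6, 5.6.1). A combined lipid summary for those patients is optional (SAP 5.7.2).

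**The concern.** All patients who stay in the trial end up on evinacumab, but a third of them start 12 weeks later than the rest. A natural reading of the safety endpoint is the share of evinacumab-treated patients who ever had a given event from their first evinacumab dose. In a trial of at most about 50 patients, that is a figure most readers will look for, and no planned table contains it.

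Two consequences follow. A reader who tries to combine the period columns will double-count patients with events in both, or will use the wrong denominator. And in the single-blind all-patients row for time to first infusion reaction, time zero is a first evinacumab infusion for some patients and a fourth for others.

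**Working it through.** **Inputs.** Dose days 1, 29, 57 and then 85, 113, 141 (Protocol 7.6). Randomisation 2:1, up to about 50 patients (SAP 2.1). Event windows (SAP 4.8.1). Drop-out 20% (SAP 2.2). The documents do not say when drop-out falls; I assume that all of it comes before day 85 and is equal in both arms, and I set it against no loss.

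**The plan's own figure.** No figure is stated for safety. The 20% comes from the triglyceride sample size, which reproduces: 24 / (1 − 0.20) = 30.

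**Denominators.** Ever on evinacumab = double-blind evinacumab patients + former-placebo patients who enter the single-blind period.

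| Column | N=50, no loss | N=50, 20% loss | N=30, 20% loss |
|---|---|---|---|
| Double-blind evinacumab | 33 | 33 | 20 |
| Single-blind, former evinacumab | 33 | 26 | 16 |
| Single-blind, former placebo | 17 | 14 | 8 |
| Single-blind, all | 50 | 40 | 24 |
| Ever on evinacumab (not planned) | 50 | 33 + 14 = 47 | 20 + 8 = 28 |

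With loss, no planned column has the ever-treated denominator. Without loss, the single-blind total has it, but its numerator omits events that evinacumab-first patients had only in the double-blind period.

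**Numerators.** Take N=50 with 20% loss and assumed counts of 10/33 (30.3%), 8/26 (30.8%) and 4/14 (28.6%); the single-blind total is then 12/40 (30.0%). The tables do not show how many of the 8 are also among the 10.

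- Complete overlap: (max(10, 8) + 4) / 47 = 14/47 = 29.8%.
- No overlap: (10 + 8 + 4) / 47 = 22/47 = 46.8%.

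The same tables fit both.

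**Windows.** For a patient who continues, the double-blind window is day 1 to the day before the first single-blind dose, nominally 84 days or 12 weeks. The single-blind window ends at day 141 + 168 = day 309, so it spans 309 − 85 = 224 days or 32 weeks. SAP 5.8 plans crude percentages without patient-time, so the two sets of columns are not on the same footing.

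**Reaction clock, evinacumab-first patients.**

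| Evinacumab dose | Day | Days since first evinacumab | Days on single-blind clock |
|---|---|---|---|
| 4 | 85 | 84 | 0 |
| 5 | 113 | 112 | 28 |
| 6 | 141 | 140 | 56 |

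A patient who already reacted in the double-blind period can have a second reaction counted as first. For former-placebo patients, day 85 is the first evinacumab dose and the clock is right.

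**The case against.** The strongest reply is that the endpoint does not expressly ask for one cumulative figure, and that the plan does report incidence on evinacumab: in the double-blind evinacumab column and in single-blind columns where everyone is on drug. A reader might infer that the safety endpoint is never produced. The documents do not support that; only the cumulative per-patient figure is missing.

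A reader might also infer that fourth-dose reactions pass for first-dose ones, or that the onset pattern is wrong for the two thirds randomised to evinacumab. That goes too far as well. SAP 5.8 splits single-blind safety by former arm, so doses 4 to 6 and doses 1 to 3 can be told apart. The double-blind analysis times doses 1 to 3 correctly, and SAP 5.8.2 states which origin it uses. What remains is the all-patients timing row and the possible second first reaction.

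Nor should one claim that the single-blind total hides a first-exposure risk. Suppose 33 and 17 patients, no loss, a 15% risk in the first 12 evinacumab weeks and 5% in the next 12, independent. The single-blind total is (33×0.05 + 17×0.15)/50 = 8.4%, and ever-on-evinacumab incidence is (33×(1 − 0.85×0.95) + 17×0.15)/50 = 17.8%. But the planned split columns would show 15%, 5% and 15%, so the early risk is visible. The 17.8% is a different quantity rather than a corrected one, and the sum ignores the 32-week window.

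Two further points stand. The protocol's single treatment period starts at the first randomised dose, placebo included, so it is no precedent for an evinacumab anchor. And patient listings (Protocol 10.4.5.1; SAP 5.8.1 for serious events and discontinuations) would let someone trace repeat events by hand in a trial this small. The gap is in the tables, not in the data.

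**Conclusion.** The point holds as a limited gap in reporting. The planned tables give incidence on evinacumab by period, but not per-patient incidence over all evinacumab exposure, and the latter cannot be recovered from them. The possible error depends on how far the same patients have events in both periods: in the illustration the range is 29.8% to 46.8%, which rests on assumed counts and an assumed 20% loss before day 85. The 12- against 32-week windows and the 84-day offset follow from the nominal schedule and need no such assumption.

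This does not affect the placebo-controlled double-blind comparison, and safety here is descriptive. It is a cheap improvement worth making before the SAP is final.

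**What to change.** In SAP 5.8.1 and 5.8.2:

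- Add a supplementary all-evinacumab column: every patient with at least one evinacumab dose, each counted once per event from first evinacumab dose to the end of the treatment-emergent period, with patient-time. For evinacumab-first patients this joins the two existing windows; for placebo-first patients it is the single-blind window.
- In that column, measure time to first infusion reaction from first evinacumab dose.
- Tabulate infusion reactions by evinacumab infusion number.
- Keep all by-period tables, with the double-blind period as the controlled comparison.

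Extend this to the potentially clinically significant laboratory values in SAP 5.8.5 only with a stated baseline for former-placebo patients, namely the last value before first evinacumab dose. SAP 4.8 and 6.1 fix baseline before the first double-blind dose, and many criteria in Appendix 10.3 depend on baseline.

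The cost is one extra column in the main adverse-event tables, one short infusion-reaction table, and the baseline decision if laboratory values are included. No new data are collected. The downside is that the pooled column has no concurrent control and mixes follow-up lengths: nominally (309 − 1)/7 = 44 weeks for evinacumab-first and 32 weeks for placebo-first patients who receive all doses. That is why patient-time should stand beside it.

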5.8.1. Adverse Events

In general, the primary focus of AE reporting will be on TEAEs summarized in respective TEAE periods, specifically the DBTP and SBTP. Post-treatment AEs will be summarized separately.

If an AE onset date (occurrence, worsening, or becoming serious) is incomplete, an imputation algorithm will be used to classify the AE as pre-treatment, treatment-emergent, or post-treatment. The algorithm for imputing date of onset will be conservative and will classify an AE as treatment-emergent unless there is definitive information to determine pre-treatment or post-treatment status. Details on classification of AEs with missing or partial onset dates are provided in [Section 6.2](#).

Adverse event incidence tables will present the number (n) and percentage (%) of patients experiencing an AE by SOC and PT. Multiple occurrences of the same event in the same patient will be counted only once in the tables within a treatment phase (TEAE or post-treatment AE). For tables presenting severity of events, the worst severity will be chosen for patients with

multiple instances of the same event. The denominator for computation of percentages is the respective safety analysis set within each treatment group.

AE incidence tables will present data by SOC sorted alphabetically and PT sorted by decreasing frequency of the evinacumab treated group and summarize the number (n) and percentage (%) of patients experiencing an AE.

Analysis of all treatment-emergent adverse events

The following TEAE summaries will be generated:

- Overview of TEAEs, summarizing number (%) of patients with any
 - TEAE;
 - Serious TEAE;
 - TEAE leading to death;
 - TEAE leading to permanent treatment discontinuation.
- All TEAEs by primary SOC and PT
- Number (%) of patients experiencing any TEAE(s) presented by primary SOC and PT
- All TEAEs relationship (related/not related) to evinacumab
- All TEAEs by maximum severity (i.e., mild, moderate or severe)

Analysis of all treatment emergent serious adverse event(s)

- All Serious TEAEs by primary SOC and PT
- Patient listings of serious TEAEs will be provided in the report appendix
- All Serious TEAEs relationship (related/not related) to evinacumab

Analysis of all treatment-emergent adverse event(s) leading to treatment discontinuation

- All TEAEs leading to permanent treatment discontinuation, by primary SOC and PT
- Patient listings of TEAEs leading to permanent treatment discontinuation will be provided in the report appendix

Post-treatment adverse events

- All post-treatment AEs by primary SOC and PT
- All post-treatment SAEs by primary SOC and PT

Patient Deaths

The following summaries of deaths will be generated.

- Number (%) of patients who died by study period (TEAE and post-treatment) and reason for death;
- TEAEs leading to death (death as an outcome on the AE CRF page, as reported by the Investigator) by SOC and PT.

Hepatic Disorder

Hepatic disorder events will be defined using the SMQ drug-related hepatic disorder (comprehensive search).

- All hepatic disorder TEAEs by PT

5.8.2. Analysis of Adverse Events of Special Interest

Treatment-emergent adverse events of special interest (AESI), as listed in Section 4.8.1.2, will be presented by SOC and PT, if applicable. AESI are defined by SMQ, CMQ, dedicated e-CRF, or lab data as described in [Appendix 10.2](#).

The following variables will also be tabulated for infusion reactions TEAEs:

- Intensity of the event (mild, moderate, and severe);
- Number of events divided by the number of study treatment administrations received in respective treatment periods;
- Time from first study treatment administration (DBTP or SBTP depending on the analysis) to first infusion reaction;

5.8.3. Analysis of Incidence of Recurrent Acute Pancreatitis

Acute pancreatitis event incidence table will present the number (n) and percentage (%) of patients experiencing such event. Multiple occurrences of the same event in the same patient will be counted only once in the tables within a treatment phase (TEAE or post-treatment AE). The denominator for computation of percentages is the respective safety analysis set within each treatment group.

5.8.4. Analysis of Hospitalizations

Hospitalizations event (defined in Section 4.8.1.5) incidence table will present the number (n) and percentage (%) of patients experiencing such event. Multiple occurrences of the same event in the same patient will be counted only once in the tables within a treatment phase (TEAE or post-treatment AE). The denominator for computation of percentages is the respective safety analysis set within each treatment group.

5.8.5. Clinical Laboratory Measurements

For respective treatment period (DBTP and SBTP), clinical laboratory parameter actual values (quantitative) and change from baseline values will be descriptively summarized at baseline and each post-baseline visit (collected up to the day of last dose of study treatment +28 days) by at least patient number, mean, median, Q1, Q3, SD, minimum and maximum. Clinical laboratory parameters mean changes from baseline, with the corresponding SE, can be plotted at each visit in the case results warrant further investigation. These parameters will be presented by the biological functions defined in Section 4.8.2. For glucose, only fasting samples will be included in the summaries.

Individual patient laboratory parameter measurements will be additionally evaluated by PCSV criteria (See [Appendix 10.3](#)), specifically identifying patients with at least one post-baseline

measurement that meets the PCSV criteria within the respective TEAE periods. These laboratory parameters will be presented by the biological functions defined in Section 4.8.2. The incidence of PCSVs at any time during the respective TEAE periods will be summarized regardless of the baseline level, and again according to the following baseline categories:

- Normal (according to PCSV criterion/criteria)/missing
- Abnormal according to PCSV criterion or criteria

Patient listings of laboratory measurements that meet PCSV criteria will be provided for the report appendix. For those laboratory parameters that don't have an associated PCSV criteria, similar summary tables can be provided based on measurements outside the central laboratory normal ranges, if applicable.

Drug-induced liver injury

For respective treatment period (DBTP and SBTP), an evaluation of drug-induced serious hepatotoxicity (eDISH) with the graph of distribution of peak values of ALT versus peak values of total bilirubin will also be presented using post-baseline values during respective TEAE periods. Note that the ALT and total bilirubin values are presented on a logarithmic scale. The graph will be divided into 4 quadrants with a vertical line corresponding to 3 x ULN for ALT and a horizontal line corresponding to 2 x ULN for total bilirubin.

Patient listing of possible Hy's law cases identified by treatment group (i.e., patients with any elevated ALT >3 x ULN, and associated with an increase in bilirubin >2 x ULN, concomitantly or not) with ALT, AST, ALP, total bilirubin, and if available direct and indirect bilirubin will be provided.

